9.4.4.9. Change in target limb TBI at 4 and 7 months

Change in TBI at 4 and 7 months will be analyzed in a manner similar to the repeated measurement models described in Section 9.4.4.23 with the baseline TBI values as the covariate. An additional fixed factor for the method of toe pressure assessment used (Doppler vs PPG) will be added to the models. TBI results for a subject will be omitted from the analysis if the same method was not used for all his/her toe pressure assessments.

9.4.4.10. Change in each domain score of CWIQ at 4 months and 7 months

Descriptive statistics of each CWIQ domain score and overall Quality of Life scores will be summarized by treatment group at each visit (baseline, 4 months, and 7 months). Change in each CWIQ score at 4 and 7 months will be analyzed in a manner similar to the repeated measurement models described in Section 9.4.4.23 with the baseline score as the covariate.

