4.2.7. COPIES OF VM202 IN WHOLE BLOOD

The number of copies of VM202 in whole blood will be determined by PCR at Day 0 (pre-injection, and 2 hours $[\pm 1 \text{ hour}]$ post injection), at Day 14 (pre-injection, and 2 hours $[\pm 1 \text{ hour}]$ post injection), Day 28 (pre-injection, and 2 hours $[\pm 1 \text{ hour}]$ post injection), Day 42 (pre-injection, and 2 hours $[\pm 1 \text{ hour}]$ post injection), Day 60, and Day 90.

Six (6) cc of whole blood will be collected in EDTA-coated tubes, inverted >5 times and transferred to plastic sterile and or RNase and DNase free vials of ~0.6 − 1 cc aliquots each for a total of 5 aliquots per time point. These will be maintained in a ≤ --65°C freezer until shipped for analysis. Samples should be labeled with study number, subject ID, draw date and time, and visit interval (i.e., Day 0 pre, Day 0 post, Day 14 pre, Day 14 post, Day 28 pre, Day 28 post, Day 42 pre, Day 42 post, Day 60, and Day 90).

At the request of the Sponsor or its designee, VM202 samples will be batched with serum HGF samples and shipped in a special container with temperature tracking recorder to analysis.

Note, will provide collection tubes, plastic vials, labels, shipment materials including temperature tracking devices to each participating site for use during the study.

4.2.8. ANKLE BRACHIAL INDEX (ABI), TOE BRACHIAL INDEX (TBI) AND TOE PRESSURE IN THE TARGET LIMB

Ankle-Brachial Index (ABI) and Toe Brachial Index (TBI) will be determined in the target limb at Screening, before the first treatment (injection) on Day 0, Day 120 (4 months) and Day 210 (7 months). Toe pressure will be determined at Screening in the target limb. Instructions can be found in Appendix 6.

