- 7. Watch the Doppler probe while inflating the cuff; not the sphygmomanometer. This will ensure that the probe is not inadvertently moved, thereby losing the pulse.
- 8. Inflate the cuff about 20 mmHg above the last audible pulse sound.
- 9. Turn attention to the sphygmomanometer and deflate the cuff slowly (about 2 mmHg per second). Record the reading of the first sound you hear that you are confident is a pulse sound.
- 10. Wait twenty seconds, with the cuff completely deflated. Repeat steps 4 through 9 to obtain a second pressure at each vessel. Use the average of the two measurements to define a single pressure for each vessel. If individual pressures for a vessel are ≥ 10 mmHg different from each other, repeat the process until the difference between the pair of systolic pressures is < 10 mmHg.

Performing a Resting TBI

- 1. Resting TBI measurements must be taken after the subject has rested for at least 10 minutes in the supine position.
- 2. Resting TBI pressures should be obtained in a horseshoe shape starting with right arm and finishing with the left arm (brachial pressures should be obtained even if previously obtained for ABI measurements).
- 3. Use arm cuff appropriate to the size of the arm being tested.
- 4. Position cuff so the middle of the bladder is over brachial vessel & wrap cuff tight enough so that no more than two fingers can be inserted between the cuff and the arm.
- 5. Use an adequate amount of gel.
- 6. Use Doppler (not a stethoscope).
- 7. Search for strongest pulse, prior to inflating the cuff (do not use first sound heard).
- 8. Keep hand and Doppler stabilized (i.e., on bed, subject, etc.).
- 9. Watch Doppler hand while inflating cuff.
- 10. Inflate approximately 20mm above last heard pulse.
- 11. Deflate cuff slowly, approximately 2mm every second.
- 12. Record the reading of the first sound you hear that you are relatively certain is a pulse sound.
- 13. Deflate cuff and wait at least 20 seconds.
- 14. Repeat steps 1 through 13 on the same vessel. Use the average of the two measurements to define a single pressure for that vessel.
- 15. If the first and second readings are 10mm or more different from each other, discard both readings and restart the assessment of the pressure of this vessel.

Toe Pressure (using a photoplethysmography [PPG]):

- 1. Apply double-sided clear tape over the pad of the big toe
- 2. Use a toe cuff

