4.2. Other Efficacy Endpoints

- Time to complete wound closure of foot ulcer
- Proportion of subjects with a target wound closure by 7 months
- Percent change in wound volume at 2 months (Day 60), 2.5 months (Day 74), 3 months (Day 90), 4 months (Day 120), and 7 months (Day 210)
- Percent change in wound perimeter, area and wound depth at 2 months, 2.5 months, 3 months, 4 months, and 7 months
- Proportion of subjects with formation of new ulcers on the target foot by 2 months, 2.5 months, 3 months, 4 months, and 7 months
- Time to major amputation in the target limb
- Time to minor amputation in the target limb
- Change in target limb ABI at 4 months and 7 months
- Change in target limb TBI at 4 months and 7 months
- Change in TcPO₂ at 4 months and 7 months
- Change in the overall quality of life and each domain score (well-being, physical symptoms and daily living, social life) of CWIQ from Day 0 at 4 months and 7 months

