5.4. Derived Variables

Baseline Value

The last non-missing value prior to first dose of study drug. If a subject does not receive any study drug, baseline is the latest recorded measurement on or before the randomization date.

Change from Baseline Value

Change from baseline value is the arithmetic difference between a value of interest and a baseline value: Change from baseline value = (value of interest – baseline value).

Percent Change from Baseline Value

The ratio of the arithmetic difference between a value of interest and the baseline value to the baseline value multiplied by 100: (Change from Baseline / Baseline) \times 100.

Time to Complete Wound Closure

Time to complete wound closure is the time interval (in days) from Day 0 to the date of the first visit date within the allowed visit window where wound closure is so indicated by the investigator. If a subject has not experienced complete wound closure, the subject will be considered censored at the subject's end of study date.

Time to a major amputation in the target limb

Time to a major amputation in the target limb is the time interval (in days) from Day 0 to the earliest date of a reported AE of an amputation of the lower extremity above the ankle of the target limb.

Time to a minor amputation in the target limb

Time to a minor amputation in the target limb is the time interval (in days) from Day 0 to the earliest date of a reported AE of an amputation of a foot or any parts of a foot such as toes on the target limb.

Absolute Differentials

If not provided by the individual study center labs, values for the absolute differentials (i.e., neutrophils, lymphocytes, monocytes, eosinophils, and basophils) will be calculated by multiplying the WBC count by the corresponding percent differential in the total WBC count. Results should be rounded to the nearest hundred for units equivalent to $10^3/\mu L$.

Percent Differentials

If not provided by the individual study center labs, values for the percent differential (i.e., neutrophils, lymphocytes, monocytes, eosinophils, and basophils) will be calculated by dividing the corresponding absolute differential count by the total WBC count. Results should be rounded to the tenth of a percentage point.

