9.4.4. Other Efficacy Endpoints

All the exploratory efficacy analyses will be based on the available data in the ITT population.

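### The TBI analysis drops all of a subject's results when the toe-pressure method differed at any assessment, so changes measured with one method at both ends are lost

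*SAP*

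**What the plan says.** SAP 4.2 lists the endpoint as "Change in target limb TBI at 4 months and 7 months", so each subject can contribute two changes. SAP 5.4 defines baseline as "The last non-missing value prior to first dose of study drug", which is the Day 0 value when there is one and the Screening value otherwise.

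Protocol 4.2.8 and Appendix 6 schedule TBI at Screening, Day 0, Day 120 and Day 210. Toe pressure as a measurement of its own is scheduled once: "Toe pressure will be determined at Screening in the target limb". Appendix 6 describes toe pressure by either PPG or Doppler; its TBI instructions name Doppler only.

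SAP 9.4.4.9 analyses TBI change with a repeated-measures model. It cites a section 9.4.4.23, which does not exist; I take it to mean 9.4.4.3. Two provisions deal with method. The first is a model term: "An additional fixed factor for the method of toe pressure assessment used (Doppler vs PPG) will be added to the models". The second is the exclusion: "TBI results for a subject will be omitted from the analysis if the same method was not used for all his/her toe pressure assessments". The unit removed is the subject, not the visit or the single change, and no section offers a visit-level alternative. The general rule in SAP 9.4.4 is "All the exploratory efficacy analyses will be based on the available data in the ITT population".

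**The concern.** A difference in method can distort a change only when it lies between the two measurements that form that change. The exclusion reaches further: one discordant assessment anywhere removes both changes, including one whose baseline and follow-up were measured the same way.

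The model does not need this. A repeated-measures model with visit and treatment-by-visit terms can use a subject who has one of the two follow-up values, and SAP 9.4.4 otherwise works from available data. At stake is the precision of the TBI comparison in a trial that enrolled 7 + 5 + 16 + 16 = 44 subjects (SAP 1) against a planned 300.

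**Working it through.** The plan states no figure to reproduce. The check has two parts: what the rule deletes, and an illustration of how much that could be.

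**1. What the rule deletes.** Write D for Doppler and P for PPG.

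*Three assessments (Day 0, Day 120, Day 210).* There are 2³ = 8 patterns. The rule keeps DDD and PPP and drops 6. In 4 of the 6 (DDP, PPD, DPD, PDP) one change has the same method at both ends: the Day 120 change in the first two, the Day 210 change in the last two. In DPP and PDD neither change is consistent.

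*Four assessments (Screening added in front).* There are 2⁴ = 16 patterns. The rule keeps 2 and drops 14. In 10 of the 14 at least one change is consistent. In 2 of those 10 (DPPP and PDDD, where only Screening differs) both changes are consistent and both are lost.

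These are counts of patterns, not frequencies.

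**2. Illustrative size.** Assume each assessment independently uses the less common method with probability q. This q is an assumption; the documents give no rate.

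- Subject dropped, k assessments: 1 − [(1 − q)^k + q^k]
- Change value lost under pair matching: 2q(1 − q)

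| q | Dropped, k = 3 | Dropped, k = 4 | Change values lost, pair matching |
|---|---|---|---|
| 5% | 1 − (0.857375 + 0.000125) = 14.3% | 1 − (0.814506 + 0.000006) = 18.5% | 2 × 0.05 × 0.95 = 9.5% |
| 10% | 1 − (0.729 + 0.001) = 27.0% | 1 − (0.6561 + 0.0001) = 34.4% | 2 × 0.10 × 0.90 = 18.0% |

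Dropping a subject also drops that subject's Day 120 change. The difference between the columns is therefore the share of Day 120 changes that are consistent and yet discarded. With 44 subjects and complete data:

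- k = 3: (14.25% − 9.5%) × 44 = 2.1 at q = 5%; (27.0% − 18.0%) × 44 = 4.0 at q = 10%
- k = 4: (18.5% − 9.5%) × 44 = 4.0 at q = 5%; (34.4% − 18.0%) × 44 = 7.2 at q = 10%

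By symmetry the same holds for Day 210. At q = 0 the rule costs nothing.

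**The case against.** The strongest defence is that this is a deliberate, conservative comparability rule. It is prespecified, depends on method and not on outcome, favours neither arm on its face, and keeps the Doppler/PPG factor constant within a subject. The endpoint is one of many exploratory ones. That defence stands as to consequence, but not as a reason for whole-subject deletion. If every retained change matches its baseline method, the factor is still constant within subject, so nothing in comparability is given up.

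Four stronger readings are tempting, and the documents do not support them.

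- *That the SAP expressly counts Screening.* It does not name Screening. Coverage follows only from taking the word *all* literally alongside the protocol schedule. The sentence can also be read as limited to the values that enter the analysis. The Day 120/Day 210 problem exists on either reading. On the literal one, a PPG toe pressure at Screening followed by Doppler TBI throughout would follow Appendix 6 and still trigger exclusion.
- *That 14-27% or 19-34% of subjects will be lost.* These percentages come wholly from an assumed rate and assumed independence. Equipment is probably fixed by site, which would make switching within a subject rarer and clustered.
- *That the repair ends exclusion based on post-randomization events.* Pair matching also excludes values according to the method used at follow-up. The dependence is reduced, not removed.
- *That the repair has no downside.* The subjects contributing at Day 120 and at Day 210 may then differ because of method. The repeated-measures model accommodates this, but the report should show the numbers at each visit.

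**Conclusion.** The point holds in limited form. As written, SAP 9.4.4.9 discards method-consistent TBI changes because of a different method at a visit that plays no part in them. This is certain for Day 120 against Day 210, and extends to Screening on a literal reading.

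The effect is lost precision on an exploratory endpoint. The omission applies to the TBI analysis only; the primary endpoint and the other analyses are untouched. The number of subjects affected is unknown. Under the assumed 5-10% independent switching, about 2 to 4 consistent Day 120 changes among 44 subjects would be discarded if three assessments count, and about 4 to 7 if four do. A reader should not infer that the TBI result would be biased or that any trial conclusion would alter. This is a worthwhile clarification, not the correction of a serious error.

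**What to change.** Replace the exclusion sentence in SAP 9.4.4.9 with a rule per change: omit a TBI change value only if the method at that follow-up visit differs from the method of the baseline value used, and disregard the Screening method unless Screening supplies the baseline under SAP 5.4. Keep the method factor. The whole-subject rule may be retained as a sensitivity analysis. Report, by arm and visit, how many change values were omitted for method.

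The cost is one SAP sentence, best made before unblinding, and one small table. No further data are needed, because the present rule already requires the method at each assessment. The price is possibly different contributing subjects at the two visits. In the same edit, state which readings count as toe-pressure assessments, and reconcile the Doppler-only TBI instructions in Appendix 6 with the Doppler/PPG factor in the SAP.

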9.5. Safety Analyses

No formal statistical testing will be conducted for the safety analyses. The following sections summarize the descriptive analysis presented for these safety endpoints. All subjects in the safety population will be included in these analyses, with subjects grouped by the actual treatment received. All summaries will be derived based on available data at scheduled visits; safety data at unscheduled visits will only be included in data listings. No imputation will be performed for missing values.

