3.5.2. DISCONTINUED SUBJECTS

Any subject may voluntarily discontinue the study at any time without prejudice. The investigator may discontinue a subject from the study at any time if (s)he considers that remaining in the study compromises the subject's health or the subject is not sufficiently cooperative. In either event, reason(s) for discontinuation should be recorded on the study worksheets.

Possible reasons for study discontinuation include the following:

- Adverse events necessitating discontinuation from the study.
- The subject is lost to follow-up.
- Subject decision (specify).
- Investigator decision (specify).
- Other reason (specify).

The reasons for any subject discontinuation will be recorded on the study completion form of the study worksheets.

Additional subjects may be enrolled if subjects discontinue prior to the 4 Month visit in order to achieve a 300-subject dataset with 4-month data.

Subjects discontinued for AE(s) will be followed-up after subject's discontinuation until the event is resolved or considered medically stable by the investigator.

Subjects that withdraw after receiving any treatment injections but prior to study completion will undergo the following, if possible:

- Vital signs
- Concomitant medications
- Documentation of the target ulcer (photograph and measurements of surface area, depth, perimeter and volume) before and after debridement.
- Serum chemistry and hematology
- Serum HGF if discontinued prior to Day 90
- Copies of VM202 in whole blood if discontinued prior to Day 90
- Injection site reaction assessment if discontinued prior to Day 60
- Adverse event assessment

In case of a subject lost-to-follow-up, the investigator/designee must do his/her best to contact the subject (by phone or letter) at least twice. If no response is obtained from the subject, the investigator is encouraged to contact one of the subject's

relatives or his/her general practitioner. Documentation of these contacts must be recorded in the subject medical chart. It can be, for instance, the acknowledgement of receipt of a letter sent to the subject.

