8.2. Visit Windows

Data at each scheduled follow-up visit will be analyzed according to the nominal visit identified on the data record. In case of multiple different visits identified with the same nominal visit, the visit with the visit date closest to the target days of each protocol-specified visit schedule (Table 5) will be used for the efficacy analyses of exploratory endpoints assessed at specific months. For visits with the same distance to the target days, the later nominal visit record will be used. Data from the other visits (if any) will be provided in data listings.

Table 5 Target Day and Month Descriptor

	1 st INJECTION	2 ND INJECTION	3 RD INJECTION	4 TH INJECTION	DAY 60	DAY 74	DAY 90	DAY 120	DAY 210
TARGET DAY	0	14	28	42	60	74	90	120	210
FOLLOW-UP MONTH	-	-	-	-	2	2.5	3	4	7

Data from 'weekly wound assessment and dressing change', 'confirmation of ulcer healing', 'early withdrawal', and any unscheduled study visits will be used in addition to the scheduled target day visits to determine efficacy endpoints that are the response rate by a given follow-up visit (e.g., the primary efficacy endpoint) or a time to event endpoint (e.g., time to complete wound closure).

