9.5.4. Vital Signs

Vital signs and change from baseline will be summarized descriptively at each visit by treatment group. Note that weights were not collected at the weekly 'wound assessment and dressing change' visits nor at the 'confirmation of ulcer healing' visit for subjects enrolled under protocol version D or later; weights collected at such visits from subjects enrolled prior to protocol version D will be included in listings only.

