9.5.5. HbA1c, Serum Chemistry and Hematology

Shift tables (i.e., normal or abnormal at baseline versus normal or abnormal at follow-up in a 2-by-2 contingency table) based on the normal range will be provided to assess changes in laboratory values from baseline to follow-up results for each scheduled follow-up visit. Additionally, shift tables of severity (low, normal, high) at baseline vs low, normal and high at each scheduled follow-up visit will also be summarized for hematology and chemistry parameters. Low and high severities are with respect to the lower and upper limits of normal, respectively, while normal is within normal limits. The counts and percentage of subjects with each of the 4 possible "shift" outcomes will be calculated by treatment group.

Individual laboratory parameter values and changes from baseline will be summarized descriptively by treatment group at each scheduled follow-up visit.

Laboratory values and their center-specific normal ranges will be listed and summarized using SI units. For the WBC differentials, only the absolute values will be summarized; percent differentials, if provided by the study center, will be listed only.

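### SAP 9.5 sends unscheduled-visit safety data to listings, leaves early-withdrawal data unclassified and plans no worst-post-baseline summary, so some post-dose abnormalities may never be tabulated

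*SAP*

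**What the plan says.** The general rule is in SAP 9.5: "All summaries will be derived based on available data at scheduled visits", and "safety data at unscheduled visits will only be included in data listings". Protocol 6.3.3 has the corresponding statement on available data but does not mention scheduled visits.

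SAP 9.5.5 applies the rule to laboratory data. Shift tables are provided "to assess changes in laboratory values from baseline to follow-up results for each scheduled follow-up visit", and "Individual laboratory parameter values and changes from baseline will be summarized descriptively by treatment group at each scheduled follow-up visit". No summary of the worst or last post-baseline value is described.

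SAP 9.5.4 is worded differently: "Vital signs and change from baseline will be summarized descriptively at each visit by treatment group". The only vital-sign data it sends to listings by name are certain weights from weekly and healing-confirmation visits: "weights collected at such visits from subjects enrolled prior to protocol version D will be included in listings only".

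On early withdrawal, Protocol 3.5.2 states: "Subjects that withdraw after receiving any treatment injections but prior to study completion will undergo the following", where possible. The list that follows includes vital signs, serum chemistry and hematology. The visit has its own column in Protocol Appendix 1 and in SAP Tables 1 to 3, but no target day in SAP Table 5.

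For efficacy, SAP 8.2 is more inclusive. Weekly, healing-confirmation and early-withdrawal data and "any unscheduled study visits will be used in addition to the scheduled target day visits" when response rates by a given visit and times to event are derived.

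**The concern.** Safety is one of the two objectives in SAP section 2. Repeat tests are often ordered because something looks wrong, and a withdrawal visit may be the last look at a subject who stopped for a safety reason. If those results are only listed, the tables that a reader uses to compare the arms can omit the observations of most interest. The plan also treats the two kinds of outcome differently without explanation: an unscheduled visit can establish wound closure for the primary endpoint, but an abnormal laboratory value from the same visit would not enter a laboratory table. What is at stake is the completeness of the descriptive safety tables. Alpha, power and the primary analysis are not involved.

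**Working it through.** The plan states no figure to reproduce, so the check compares the sections and then follows the visit calendar.

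**1. Protocol against SAP.** Protocol 6.3.3 uses the data available and imputes nothing. SAP 9.5 also imputes nothing but restricts the data to scheduled visits. The SAP is narrower than its protocol and gives no reason.

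**2. When can a post-dose laboratory value enter a table?** Protocol 4.2.5 schedules chemistry and hematology at Screening and Days 0, 42, 90, 120 and 210. The Day 0 sample is drawn before injection (Protocol 3.4.8.1), so the post-dose samples fall on Days 42, 90, 120 and 210. The Day 42 sample is drawn before the fourth injection (Protocol 3.4.12.1). By nominal day:

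| Interval | Length | Injections given at the start of or within the interval |
|---|---|---|
| Day 0 to 42 | 42 days | Days 0, 14 and 28 |
| Day 42 to 90 | 90 − 42 = 48 days | Day 42 |
| Day 90 to 120 | 120 − 90 = 30 days | none |
| Day 120 to 210 | 210 − 120 = 90 days | none |

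Three of the four injections are therefore given before the first scheduled post-dose sample. A chemistry or hematology result obtained between these days can come only from an unscheduled or an early-withdrawal visit.

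**3. Unscheduled visits.** The rule is explicit: listings only. With no worst-value summary, nothing brings a post-dose repeat value back into a laboratory table.

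**4. Early withdrawal.** The text can be read two ways.
- *As scheduled:* it is a planned assessment with its own column in the schedules, and SAP 8.2 names it separately from unscheduled visits.
- *As not scheduled:* it has no target day or follow-up month in SAP Table 5, so tables built by scheduled follow-up visit have no defined place for it.

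On the second reading, a treated subject who leaves before Day 42 adds no post-baseline chemistry or hematology value to any table, although SAP 9.5 says that the whole safety population is included. A subject who leaves between Days 120 and 210 adds none after Day 120.

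**5. Vital signs.** SAP 9.5 limits summaries to scheduled visits, while SAP 9.5.4 refers to every visit. The two are not reconciled.

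**6. Adverse events as a second route.** Protocol 5.1 allows a clinically significant abnormal result to be an adverse event, and SAP 9.5.3 defines treatment-emergent events by onset after dosing, whatever the visit. But Protocol 4.2.5 says that an abnormal reading is not automatically an adverse event, and Protocol 5.1 excludes changes in keeping with natural disease progression. The route exists but does not catch everything.

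**7. Size.** SAP section 1 gives 7 + 5 + 16 + 16 = 44 subjects enrolled. No withdrawal rate is given. Purely as an assumption, 5% to 20% would be 44 × 0.05 = 2.2 to 44 × 0.20 = 8.8, or about 2 to 9 subjects. That is the number of subjects whose last visit would be in question, not the number of missed abnormalities, and it treats all enrolled subjects as dosed. The number of unscheduled repeat tests is also unknown.

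**The case against.** The strongest reply is that by-visit tables with full listings are a legitimate design. Safety is descriptive, nothing is discarded, and listings for 44 subjects can be read line by line. That stands, and it keeps the point modest. It does not explain why the SAP is narrower than the protocol, nor does it settle the early-withdrawal question.

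Several stronger readings are tempting, but the documents do not support them:

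- *Early-withdrawal results are excluded from the tables.* A reader might infer this from SAP 8.2. That section concerns efficacy and lists the visit apart from unscheduled ones. Weekly visits are in the same list, yet SAP 9.5.2 tabulates injection-site events at them, so being on the list does not remove a visit from safety tables. The exclusion is possible but not stated.
- *Vital signs from such visits are only listed.* The wording of SAP 9.5.4 points the other way, and its named exception for certain weights would be largely unnecessary if those visits were already excluded.
- *Unscheduled values never reach any summary.* A clinically significant result can enter the adverse-event tables. A pre-dose unscheduled value could also serve as baseline, because SAP 5.4 takes the last non-missing value before dosing.
- *Adverse events found at unscheduled visits are dropped.* SAP 9.5.3 is the specific section, and it defines these events by onset.
- *The tables systematically miss the worst values.* No data on withdrawals or repeat tests support this. A repeat may equally show a return to normal, and the scheduled abnormal value stays in its table.

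**Conclusion.** The point holds as a limited one and merits a change. An explicit rule keeps unscheduled-visit safety data out of the summaries, the place of early-withdrawal results is undefined, and no worst-post-baseline summary recovers either. With post-dose laboratory samples at only four nominal days, a post-dose abnormality found between them may appear only in a listing unless it is reported as an adverse event. For unscheduled laboratory values this follows directly from SAP 9.5 and 9.5.5. For early withdrawal, and for vital signs generally, it depends on how unreconciled text is read.

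The size cannot be stated. A reader might divide the 44 enrolled in the planned 2:1 ratio and express one missed abnormality as a percentage of an arm. The documents give neither the actual split nor the number treated, and by-visit shift tables may use a different denominator at each visit, so such a figure would not measure the effect.

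**What to change.** - Keep all by-visit tables as planned.
- Add to SAP 9.5.5 one worst-post-baseline shift summary per laboratory parameter, and to 9.5.4 a similar summary for vital signs. Both should use every post-dose value, including those from early-withdrawal and unscheduled visits.
- State in SAP 9.5 that the limit to scheduled visits applies to by-visit tables only. This restores agreement with Protocol 6.3.3. It also makes clear that adverse-event tables, already defined by onset in 9.5.3, include events found at any visit; they need no other change.

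The data are already collected, so the cost is a small extra table set. Worst-value summaries give somewhat higher abnormality counts than by-visit tables, and they are sensitive to unequal repeat testing: an arm tested more often has more chances to show an abnormal value. Reading them alongside the by-visit tables limits that risk.
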